### Methods

**1. Participants and Enrollment.** In each year of the project, we will recruit samples of Veterans with PLP from primary care and amputee clinics. Co-investigator [name], NP, is the PACT (Primary Aligned Care Team) coordinator in the amputee clinic at the VA San Diego Healthcare System (VASDHS) and has specific recruitment experience with the PLP population from our previous R&D-supported clinical trial for PLP.

**2. Inclusion criteria.** 1) Ages 21-75 Veteran receiving care at VASDHS; 2) Upper or lower extremity amputation with reported PLP for at least six months; 3) PLP intensity  $\geq 4/10$ ; 4) English-speaking, literate, with stable residence; 6) Able to operate a VR headset as evidenced by direct observation. **3. Exclusion Criteria.** 1) Major medical illness that might confound effects of pain on function (e.g., advanced cardiac or pulmonary disease); 2) current active alcohol or substance use disorder as evidenced from medical record; 3) currently active suicidality, homicidality, or unstable psychiatric status in previous three months as measured by direct observation, patient self-report, or medical record; 4) moderate or severe cognitive impairment as demonstrated by medical diagnosis or clinical observation; 5) Prior mirror therapy experience.

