Feasibility outcomes – including satisfaction, adherence, side effects, and mood and PLP changes – will be compared pre-to-post treatment separately for the VR and mirror therapy protocols and between the two treatments. Participants will utilize each treatment for one month. This treatment duration is consistent with periods allowing for pain symptom reductions in previous VR studies and for PLP changes in mirror therapy participants. During this phase, participants will complete in person baseline and weekly visits for four weeks with either the VR technical staff (VR) or study coordinator (mirror therapy) in addition to their daily homework exercise recommendations. Following IMMPACT (Initiative on Methods, Measurement and Pain Assessment in Clinical Trials) guidelines, the baseline and post-treatment visits will include measures of PLP (Phantom Limb Pain Questionnaire (PLPQ), adjustment to amputation and prosthesis (Trinity Amputation

and Prosthetic Experience Scale (TAPES), mood (Beck Depression Inventory), and life quality (Medical Outcomes Study (SF-12). The study coordinator will administer the assessment measures with both treatment groups. Team statistician, [name], will receive outcome data blinded to treatment assignment.

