### Study Measures

**Table 2. Timetable of Study Measures During Feasibility Trial**

Evaluation/Study Week	Baseline	Weeks 2-3	Week 4
Screening and Qualification	X		
Medical Chart History Review	X		
Dependent Variable Measures			
Phantom Limb Pain Questionnaire (PLPQ)	X	X	X
Trinity Amputation and Prosthetic Experience Scale (TAPES)	X	X	X
Pain Interference (Brief Pain Inventory, SF-12)	X	X	X
Pain Intensity (Numerical Pain Rating Scale)	X	X	X
Mood (BDI)	X	X	X
Treatment Credibility/Feasibility & side effects	X	X	X
Treatment Satisfaction		X	X
Immersiveness of mirror therapy experience		X	X

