Regarding the feasibility trial Aims 2-3, we will assess feasibility of the study and if the use of the VR and mirror therapy treatments are associated with reductions in PLP, mood symptoms, or improvements in function. We will focus on our ability to implement recruitment strategies, conducting this innovative treatment and measurements, recruitment rate, consent rate, reasons for not participating, reasons for dropping off, the rate of missing data, pattern of missing values, adherence rate and subjects satisfaction. Data analyses will proceed in stages. At first, descriptive statistics and exploratory graphing such as frequencies, means, standard deviations, box and whisker plots, stem and leaf diagrams, and scatter plots will be used to assess the distribution and normality of the data in terms of the presence of skew and/or outliers. The continuous outcome data will be transformed if necessary by using an appropriate transformation such as the log transform for skewed long tailed data. Similarly, potential covariates will also be summarized with descriptive statistics and graphs to determine the most appropriate way to treat these variables to determine if a continuous, categorical, or an interval representation is the most appropriate approach. The comparability of the two treatment groups in baseline demographic and clinical features will be tested with analyses of variance (ANOVAs) for continuous variables and Chi-square analyses for dichotomous variables. Our randomization procedure is expected to control patient and treatment variables that might be associated with outcome. Any variables on which the groups differ initially will be explored as covariates in subsequent analyses, and we will take this into account in the interpretation of the outcome. Primary analyses will be based on a hierarchical model (HLM) using an intent-to-treat method that uses all available data. The model will include a random intercept, a random effect for assessment time, and fixed effects for comparison groups and group-by-time interaction. Denominator degrees of freedom will be calculated using the Kenward-Roger small sample correction. Data will be analyzed from all randomized subjects on whom we have a baseline assessment and at least one post-baseline evaluation. All hypothesis tests will be two-sided with alpha set at .05 and a medium to large effect size (i.e., Cohen's  $d \geq 1.0$ ) for changes from baseline to treatment. We will control Type I error by reducing measures to one key variable or a total or composite score when possible and will use Bonferroni correction for secondary outcomes in a domain family and secondary analyses. Using statistical power software for independent sample designs, an  $N$  of 10 for each treatment group and a minimum effect size of 1.0 standard deviation units of PLP (approximately two points on the PLPQ) results in an estimated power of .72 for the within group changes from pre- to post-treatment. The feasibility trial is not powered to detect between group differences. Based on our previous R&D trial, it will require several years of recruitment in a larger study to enable appropriately powered between group comparisons with a PLP sample. However, we will examine group means and standard deviations for the purpose of calculating effect sizes for a future trial application.

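### The plan's only power figure is for an uncontrolled within-arm change after selection on pain of at least 4/10, so a fall may be partly regression to the mean and is not by itself treatment benefit

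*Combined protocol and SAP*

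**What the plan says.** **Selection.** The inclusion criteria (Section B, Methods) require amputation "with reported PLP for at least six months; 3) PLP intensity" of at least 4/10. Neither the instrument nor the recall window for that rating is stated.

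**Timing.** Table 2 marks "Screening and Qualification" in the Baseline column only, beside the baseline PLPQ and Numerical Pain Rating Scale. Patient Selection and Recruitment has the coordinator contact the patient, obtain consent and then screen for PLP with the TAPES. The Year 2 section places written consent and the questionnaires in the baseline visit, yet describes those trained at that visit as already eligible and consented. No run-in or repeat baseline is described.

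**Analysis.** The Year 2 section says that outcomes "will be compared pre-to-post treatment separately for the VR and mirror therapy protocols and between the two treatments". Section C states that "All hypothesis tests will be two-sided with alpha set at .05". It gives an "estimated power of .72 for the within group changes from pre- to post-treatment", for a "minimum effect size of 1.0 standard deviation units of PLP (approximately two points on the PLPQ") with an N "of 10 for each treatment group", and adds: "The feasibility trial is not powered to detect between group differences". The primary hierarchical model contains a group-by-time interaction.

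**The concern.** A rating that must reach a threshold before a patient can enter is, on average, too high by part of its own measurement error or passing fluctuation. The next rating drifts back. If the qualifying rating is also the pre-treatment value, that drift counts as improvement.

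The Background describes PLP as mostly intermittent and able to vary from day to day, which is the setting where this can happen. Both arms receive an active treatment, so neither shows the change to expect without one. Regression to the mean is not mentioned anywhere.

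The Overview gives early efficacy and effect-size data for a larger trial as the goal, and Section C says the results will inform whether to commit further resources. A significant fall within an arm is the finding the plan is sized to produce. If part of it is artefact, that decision rests on an inflated effect. A confidence interval around the change shows imprecision but does not reveal this bias.

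**Working it through.** **1. The plan's own figure.** Inputs from Section C: n = 10 per arm, effect 1.0 SD, two-sided alpha .05, software for independent samples.
- Two-sample normal formula: power = Φ(d·√(n/2) − z), with d·√(n/2) = √5 = 2.236.
- One-sided .05: Φ(2.236 − 1.645) = Φ(0.591) = 0.72. This matches.
- Two-sided .05, as stated: Φ(2.236 − 1.960) = Φ(0.276) = 0.61. The two-sample t version gives 0.56.
- Paired t, two-sided, with the effect expressed in SDs of change: 0.80.

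So .72 is recovered with a one-sided independent-samples formula. That mismatch is a separate matter. None of these versions allows for a fall that occurs without treatment.

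**2. Inputs for the size of the bias.**
- SD 2: from the plan's equation of 1.0 SD with about two points, applied here to the unselected PLP population.
- Cutoff 4: inclusion criteria.
- Population mean 4–5: an assumption. Recruitment Feasibility expects half of Veterans with PLP to qualify on frequency and severity together, so at least half should pass on severity alone. That is only a rough anchor.
- Test–retest reliability r = .6–.8: an assumption. The documents give no value.
- Treatment effect: zero.
- One rating serves as both qualifying and baseline value: the worst case, not stated in the documents.

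**3. Closed form for continuous scores.** Expected fall = (1 − r)·SD·φ(c)/(1 − Φ(c)), with c = (4 − mean)/SD.
- Mean 4, c = 0: φ/(1 − Φ) = 0.399/0.500 = 0.798. Fall = 0.4 × 2 × 0.798 = 0.64 at r = .6, and 0.2 × 2 × 0.798 = 0.32 at r = .8.
- Mean 5, c = −0.5: 0.352/0.691 = 0.509. Fall = 0.41 at r = .6 and 0.20 at r = .8.

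**4. Simulation on the 0–10 scale.** True score plus independent error, rounded to whole points and bounded at 0 and 10; select at 4 or above; two-sided paired t at .05 in arms of 10; count significant falls.

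| Population mean | Pass the cutoff | Mean fall, r = .8 to .6 | Share of 2 points | Significant fall per arm |
|---|---|---|---|---|
| 4 | 60% | 0.29 to 0.54 | 14% to 27% | 9% to 14% |
| 5 | 77% | 0.17 to 0.33 | 8% to 17% | 5% to 7–8% |

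The nominal rate in that direction is 2.5%. Rounding lowers the effective cutoff to 3.5, which is why these falls are smaller than in step 3. The continuous version gives false improvement of 11–19% at mean 4 and 6.5–10% at mean 5.

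**5. Separate ratings.** With eligibility decided on one rating and baseline taken from another with independent error, the mean fall is 0.00 and the false-improvement rate about 2.5% in every scenario.

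**6. Between-arm contrast.** In the continuous model with one rating serving both purposes, a two-sided test of the difference in change rejects in 5.0–5.2% of null trials, because selection acts equally on both arms. Its power at n = 10 per arm and a 1.0 SD difference is 0.56 (two-sided t).

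**The case against.** **Same rating.** A reader might infer from Table 2 that the qualifying rating is the baseline PLPQ. The documents do not say so. Screening uses the TAPES, the powered outcome is the PLPQ, and a table with three time columns may use Baseline simply to mean before treatment. This stands, and it makes the size conditional. It does not remove the point: the timing is ambiguous across three places, and two ratings on the same day can share a passing fluctuation.

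**Variability.** The Background figures describe episode frequency, episode duration and intermittency, not test–retest error in PLPQ severity. The PLPQ is also described as a weekly questionnaire, so day-to-day swings do not carry over directly. This stands too. The reliability range is an assumption.

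**Larger figures.** With a population mean of 3 and r = .6, the same model gives a fall of 0.8 points and 27% false improvement. Only about 40% would then pass on severity, which fits poorly with the plan's estimate that half qualify on frequency and severity together. Those figures should not be used.

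**Feasibility aim.** Section C says effect-size estimation is not the main focus, reads the primary effect within its 95% CI, and asks only whether treatment is associated with reductions. The group-by-time term and a between-treatment comparison are already planned. It would therefore be wrong to say that the plan rests its efficacy case wholly on within-arm tests, or that its between-arm estimate is biased. What remains is that the contrast chosen for power is the unprotected one.

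**Conclusion.** The concern holds in conditional form. The only powered contrast is an uncontrolled change in patients selected on the outcome domain, so a within-arm fall can be partly regression to the mean and is not, alone, evidence of benefit.

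If one rating serves as both qualifier and baseline, with SD 2, population mean 4–5 and reliability .6–.8 on a rounded 0–10 scale, the spurious fall is about 0.2–0.5 points and false improvement about 5–14% per arm. Both are smaller if the two ratings differ, if entrants sit well above 4, or if reliability is higher. The documents do not support the inference that any observed fall would be wholly artefact: even the top of this range is about a quarter of the 2-point target.

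**What to change.** 1. Reconcile Patient Selection and Recruitment, the Year 2 visit description and Table 2. State which instrument and recall window define the 4/10 rating, take it at the coordinator's screening contact, and show it in its own Table 2 column. Do not reuse it as the model baseline; a separate PLPQ at the baseline visit supplies the pre-treatment value.
2. Report within-arm changes descriptively with 95% CIs. Base any statement about treatment effect on the planned group-by-time estimate with its CI, and say that it compares VR with mirror therapy, not either with no treatment, and is imprecise.

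**Cost.** Item 2 is wording only, but the within-arm p-values lose their role as efficacy evidence and the remaining contrast is underpowered, as the plan already concedes. Item 1 may need the qualifying rating, and possibly consent, slightly earlier than the baseline visit.
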